9.1 Recruitment

Potential participants will be contacted by the site to raise awareness of the study and offer access to study information. Contact methods include text messages, mail-outs and emails to those invited to receive their vaccination. Follow-up phone calls will be made to non-responders. Furthermore, study details will be added to the Cripps Health Centre website and promoted by Research Champions, PIC sites and other local GP practices.

9.2 Informed consent and enrolment

Patients invited for their COVID-19 booster vaccination and/or influenza vaccination as part of the national vaccine schedule that fit all other eligibility criteria will be invited to take part in the study.

The participant will have had sufficient opportunity, a minimum of 24 hours, to read and understand the contents of the PIS prior to being invited to provide informed consent, with further opportunities to ask questions and seek clarification at the consent and enrolment visit.

Each participant must give informed consent for the study and will be asked to acknowledge having read the latest approved version of the PIS and ICF before any study specific procedures are performed. Consent, randomisation, and vaccination will occur on visit 1. This will include consent, baseline blood collection, intervention administration and vaccination. The visit is not expected to take more than 60 minutes in total.

The PIS and ICF will present no less than the following information to the participant:

- The nature of and rationale for performing the study
- Implications and constraints of the protocol
- The risks and benefits involved in taking part in the trial

It will be clearly stated that there will be no provisions to supply participants with individual blood test results at any time, that the participant is free to withdraw from the study at any time, for any reason and that they are under no obligation to give the reason for withdrawal.

After giving informed consent participants will be allocated a unique study number.

9.3 Enrolment visit

- Informed consent and eligibility will be checked by the research team (PIs, research nurse or practitioner).
- Demographics and medical history will be collected.
- Participants will be randomly allocated to one of the 4 study groups in a 1:1:1:1 ratio.
- Randomisation will be performed by an electronic randomisation system.
- Participants will provide a 15ml venous blood sample for biochemical and immunological analysis. A subgroup of participants will be invited to have a maximum 60ml blood sample taken for further immunological analysis. Venous blood samples will be collected by a phlebotomy trained Research Nurse/Practitioner using a vacutainer system or syringe and butterfly.
- Participants randomised to the positive mood intervention will receive a 15 minute positive mood intervention consisting of a combination of positive mood stimuli previously shown to enhance mood in older adults. Participants will also receive information on how to access their positive mood intervention over the next 6 days. Daily reminders to complete the intervention and e-diary will be sent via secure SMS messaging and checked by the PI and/or Research Nurse. In the event a participant is unable to work the e-diary, alternatives can be provided, such as paper copies or phone calls.
- Participants randomised to standard over the counter vitamin D supplement, will be advised to buy and take this immediately prior to vaccination and once daily for the following 27 days. Reminders will be sent to complete the intervention and e-diary as for the positive mood intervention group.
- Participants will then receive their COVID-19 booster and influenza vaccination in the standard NHS clinic which will be running at the site on that day. The vaccine will not be given as part of the study and the type of vaccine, timing or method will not be impacted by their participation in the study.

Some participants, clinicians' and other stakeholders' will then be interviewed about the intervention and trial acceptability and determine the barriers and facilitators to implementing the intervention in routine care. Interviews will be conducted by telephone, video call or face-to-face at participant preference, audio-recorded (with permission) and transcribed verbatim.

At the end of the visit, participants will be given an email address and/or phone number to report any adverse events occurring in the seven days after vaccination and will also be given an emergency 24-hour telephone number held by an investigator for advice on matters related to study participation.

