18.	Development of a new product/process or the generation of intellectual property	31
19.	References	32
20.	Appendices	34
20.1	Vitamin D Supplementation	34

**University of
Nottingham**
Health Service

3. Plain English Summary

Vaccines help us prevent diseases and keep us well. Some vaccines work better than others and there are many reasons for this. It can be to do with the vaccine itself or to do with the person having the vaccine. We have already found that people who report feeling happier on the day they are vaccinated produce more antibodies in response to the vaccination. We have also found that giving people only 15 minutes of a positive mood intervention to watch before they are vaccinated improves their mood. Recent research also suggests that the amount of vitamin D in your body at the time of vaccination can affect how well vaccines work.

In this study we will conduct a small experiment in which people who are about to receive a COVID-19 or influenza vaccination, or both, will be put in one of 4 groups at random.

- Group 1 will not be offered anything other than their vaccine (this is called usual care).
- Group 2 will receive a brief positive mood intervention, which has previously been shown to improve mood on the day they are vaccinated and for a further 6 days. They will also be advised to take a single dose of a vitamin D tablet just before they are vaccinated and once daily for the following 27 days.
- Group 3 will also receive the positive mood intervention on the day they are vaccinated and for a further 6 days, but they will not take the vitamin D tablet.
- Group 4 will be advised to take a vitamin D tablet at the time of vaccination and once daily for the following 27 days.

We will ask all participants to provide 15ml blood samples before vaccination and then at 28 days and at 6 months post vaccination. This sample will help us measure antibody responses to the vaccination and determine how well people have responded. In addition, up to 20 people across all groups will be asked to provide up to a 60ml blood sample at baseline and at day 28. These samples will allow us to understand how our interventions are changing the way the immune system works.

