15 ml venous blood samples will be collected to detect antibodies to the vaccine antigens. These will be measured at baseline, 4 weeks and 6 months post-vaccine to assess intervention effects on peak vaccine responses and durability of protection. Participants will also receive a daily text message reminder with a link to the positive mood intervention and/or to take their vitamin D supplement, alongside an e-diary link to complete.

A sub-sample of up to 20 patients will be invited to have blood samples collected to explore potential cellular and humoral mechanisms at day 0 and day 28. This will entail an additional maximum 60ml blood sample on each occasion.

Interviews will be conducted with patients and health care professionals involved in the pilot trial to identify barriers and facilitators to implementing the intervention in routine care.

8. Participant identification

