9.7 Compliance

Compliance is defined as the proportion of participants that complete diary, receive at least one dose of the SARS-CoV-2 vaccine and provide a pre-vaccination and at least one post-vaccination blood sample.

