11.1 Sample Size Determination

We do not specify *a priori* sample size since we will be assessing recruitment, study procedures and retention in order to inform the planning of a larger trial at a future date. We will pause recruitment when we have a minimum of 10 participants in each arm (about 40 participants in total).

At that point we will perform an interim analysis of both the quantitative and qualitative data obtained and determine whether we have enough outcome measures to meet the primary objective. This decision will be taken by the study steering group which will comprise all of the investigators and the study co-ordinator. The decision will be based on whether the data obtained is sufficient to fully inform the design of the larger trial to follow, specifically whether the methodology is acceptable to participants and study staff and whether the intervention adherence measures are capturing data as intended. We have expertise in qualitative methodology in the study steering group.

If the group feel that we have sufficient data to achieve the primary objective, the study will be stopped and the exploratory outcome data will be analysed. If the group feel further data is needed, we will not analyse exploratory outcome data at this point and recruitment will resume until a minimum of 20 patients per arm have been recruited (about 80 participants in total). When data collection is complete, we will perform a final analysis of all primary and exploratory outcome data.

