11.3 Inclusion in analysis

Analysis will be conducted of a full data set for all participants who are deemed to have no major protocol violations that could interfere with the objectives of the study. Such a set will comprise all participants, who complete the e-diary (and consent form) and for whom post-baseline assessment of the primary outcome measure is available.

Laboratory data, such as blood samples, from all participants who enrol in the study will be included in the analysis.

**University of
Nottingham**
Health Service

12. Data management

The Chief Investigator will be responsible for all data that accrues from the study. All protocol-required information will be collected and into the CRF. CRF entries will be therefore considered source data. All other information will be entered onto their medical record and/or ISF. Source documents are original documents, data, and records from which the participant CRF data are obtained. For this study, these will include, but are not limited to, volunteer consent form, laboratory records, medical records, and correspondence. As part of the informed consent process, permission will be sought to access the participant's data from pertaining to basic demographic information and contact details.

All source data and participant files will be stored securely.

Direct access will be granted to authorised representatives from the Sponsor, host institution and the regulatory authorities to permit trial-related monitoring, audits and inspections. The study protocol, documentation, data, and all other information generated will be held in strict confidence. No information concerning the study, or the data will be released to any unauthorised third party, without prior written approval of the sponsor

Each study participant will retain the unique participant number first assigned at randomisation. Samples sent to laboratories for processing will be identified by participant number. All documents will be stored safely and securely in confidential conditions. Direct access will be granted to authorised representatives from the Sponsor and the UNHS and the regulatory authorities to permit study-related monitoring, audits and inspections. Participant name and any other identifying detail will NOT be included in any trial data electronic file.

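### Compliance (9.7) and the main analysis set (11.3) require a completed e-diary in every arm, but the protocol describes a diary only with the mood and vitamin D reminders, so usual care fails both rules as written

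*Protocol*

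**What the plan says.** **Who is sent a diary.** Section 7 (Methods) attaches the e-diary link to the intervention prompt: "Participants will also receive a daily text message reminder with a link to the positive mood intervention and/or to take their vitamin D supplement". Section 9.3 describes daily SMS reminders for the intervention and e-diary under the positive mood item, and then says of the vitamin D group: "Reminders will be sent to complete the intervention and e-diary as for the positive mood intervention group". For usual care, the Plain English Summary (section 3) says: "Group 1 will not be offered anything other than their vaccine (this is called usual care". No text assigns that arm a diary.

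**What depends on the diary.** Section 9.7 opens: "Compliance is defined as the proportion of participants that complete diary". It adds receipt of the SARS-CoV-2 vaccine, a blood sample before vaccination and at least one after. Section 11.3 first limits the analysis to participants without important protocol violations, and then defines the set: "Such a set will comprise all participants, who complete the e-diary (and consent form", together with a post-baseline assessment of the primary outcome. Neither section makes an exception by arm.

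**What does not depend on it.** The second paragraph of section 11.3 brings in laboratory data from everyone who enrols, with no diary condition.

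**The concern.** Two rules apply a condition to all participants that one of the four randomised arms is given no means of meeting. This is a gap in delivery, not a missing-data problem: it would remain if every participant in the intervention arms completed every entry.

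The consequences are limited but real. Section 11.1 says the trial will assess recruitment, study procedures and retention to plan a larger trial. A compliance figure with a built-in ceiling below 100% would misinform that planning. In usual care it would also hide the useful part, namely how many were vaccinated and returned for blood sampling. Section 11 describes the main analysis as a comparison of four groups, whereas the diary-based set in 11.3 would hold three. Finally, the two paragraphs of 11.3 give different populations without saying which outcomes each governs.

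An analysis plan can repair the definitions, but it cannot create diary data that were never collected. Whether usual care is sent a diary therefore has to be settled in the protocol.

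**Working it through.** **Inputs**

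- Allocation (section 9.3): "Participants will be randomly allocated to one of the 4 study groups in a 1:1:1:1 ratio".
- First stage (section 11.1): "We will pause recruitment when we have a minimum of 10 participants in each arm (about 40 participants in total".
- Possible second stage (section 11.1): "recruitment will resume until a minimum of 20 patients per arm have been recruited (about 80 participants in total".
- Arms described as receiving a diary (sections 7 and 9.3): mood alone, vitamin D alone, and both, so 3 of 4. This is a reading of the text, not an explicit statement.

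**Step 1: the plan's own totals.** Arms × minimum per arm: 4 × 10 = 40 and 4 × 20 = 80. Both agree with section 11.1. There is no power calculation to reproduce.

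**Step 2: the rules applied as written.**

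| | First stage | If extended |
|---|---|---|
| Usual care able to complete a diary | 0 of 10 | 0 of 20 |
| Intervention arms able to complete a diary | 3 × 10 = 30 | 3 × 20 = 60 |
| Highest possible overall compliance | 30/40 = 75% | 60/80 = 75% |
| Largest possible diary-based set | 30 of 40 | 60 of 80 |

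With equal arms, overall compliance equals 0.75 × compliance in the intervention arms. Any reported overall figure is therefore a quarter lower, in relative terms, than what those arms achieved.

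**Step 3: the same rules with the diary condition lifted for usual care, or with a diary sent to it.** The ceiling returns to 40/40 and 80/80.

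**Step 4: the two inclusion rules in section 11.3.** The first paragraph requires a completed diary and does not confine itself to non-laboratory outcomes. The second admits laboratory data from all enrolled participants. Take a usual-care participant with baseline and day-28 samples: the first paragraph excludes this person and the second includes the samples. Treating the second as an override for laboratory outcomes resolves the conflict, but the protocol does not say so.

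**The case against.** **Laboratory outcomes are protected.** Every exploratory outcome in the synopsis is a laboratory measure, and section 11.3 keeps laboratory data from all who enrol. A reader might infer from the diary rule that no comparison with usual care is possible. The documents do not support that: the antibody, neutralisation and T-cell comparisons survive. This part of the objection stands in full and limits the harm to the compliance figure and the diary-based set.

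**Usual care has no intervention to adhere to.** The primary outcome concerns acceptability of, and adherence to, the interventions, so losing usual care from an adherence set costs little. That is fair for adherence. It does not rescue section 9.7, whose definition covers all participants and also counts vaccination and blood sampling.

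**The diary's recipients are inferred.** Section 7 uses the general word participants, and Figure 1 is not available here. This stands as a caution. However, the reminder in section 7 concerns mood, vitamin D or both, which describes three arms, and sections 3 and 9.3 point the same way. If usual care is meant to have a diary, the protocol needs to say so.

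**Different diary lengths.** A reader might go further and infer that a 7-day diary is compared with a 28-day one, which would bias completion between active arms. The protocol gives courses of those lengths but states neither the diary's length nor what counts as complete. Even the direction is undetermined. Suppose the diary follows the course, days are independent and daily completion is 0.90 (all assumptions). Requiring every day gives 0.90^7 = 47.8% against 0.90^28 = 5.2%. Requiring about 80% of days (6 of 7, 23 of 28) gives 85.0% against 94.5%. No bias is shown.

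**Contamination and attendance.** A reader might also infer that vitamin D started independently in other arms goes undetected, or that unequal contact will make attendance differ. Section 9.6 measures serum vitamin D at each time point, which partly covers the first. The diary's content is not described, and nothing in the protocol establishes the second.

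**Conclusion.** The point holds in limited form. As written, sections 9.7 and 11.3 set a diary condition that usual care cannot meet. That arm scores 0% compliance and is absent from the diary-based set (0 of about 10, or 0 of about 20 if extended), and overall compliance is capped at 75%. This is a stated rule that gives a wrong result, not detail left for an analysis plan. The two inclusion rules in 11.3 also conflict and must be reconciled.

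The conclusion rests on two assumptions: that usual care is sent no diary, which is the natural reading though not an explicit statement, and that arms are close to equal in size. It does not extend to the laboratory comparisons, to a bias between active arms, or to contamination or attendance.

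Severity: should fix. This is a feasibility trial without a powered comparison, and the immunological outcomes are preserved.

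**What to change.** 1. In sections 9.7 and 11.3, limit the diary element to the arms that are sent a diary. Alternatively, state in sections 7 and 9.3 that usual care is sent one.
2. If usual care has no diary, define compliance there by vaccination and blood samples only, and report compliance by arm.
3. In section 11.3, say which outcomes each paragraph governs, and state that laboratory analyses use all randomised participants without the diary condition.
4. State how long the diary runs in each arm and what counts as complete. Report completion as entries completed out of entries expected, by arm.

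The wording-only route costs a short amendment and no extra data collection. Sending usual care a diary is a larger step: it adds daily contact to an arm defined as receiving only the vaccine, and so changes the comparator. A 28-day diary in that arm is not needed to resolve this point.

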UNHS:	University of Nottingham Health Service

**University of
Nottingham**
Health Service

6. Background and rationale

Vaccines play a critical role in reducing the burden of infectious disease in the population. However, with all vaccines there is variability in the effectiveness and durability of protection, with the greatest variability evident in older people. Previous research has shown that a range of emotional and lifestyle factors alter vaccine effectiveness including positive and negative mood^{1,2} and vitamin D status³ and that interventions which target these factors can enhance vaccine success⁴. Furthermore, there is evidence that vitamin D and negative mood may be inversely related, suggesting that an intervention which combines both adjuvants may have synergistic effects.

The proposed project would build on existing evidence which has demonstrated the benefits of positive mood and vitamin D for vaccine effectiveness. The aims would be to:

1. Adapt an existing brief single session positive mood intervention to permit delivery of multiple sessions in the seven days post-vaccination
2. Assess the feasibility and acceptability of vitamin D supplementation for 28 days and a brief positive mood intervention for 7 days in older adults.
3. Gather preliminary evidence on the effects of positive mood alone, vitamin D alone and positive mood and vitamin D in combination on the antibody response to influenza and SARS-CoV-2 virus vaccines
4. Investigate the cellular and humoral immune mechanisms mediating intervention effects

**University of
Nottingham**
Health Service

7. Methods

Patients aged 65 years or greater being targeted for COVID-19 and/or influenza vaccination will be recruited from primary care to participate in a feasibility trial. They will be randomly allocated on a 1:1:1:1 basis to receive:

- No intervention (Usual Care)
- Positive mood intervention on the day of vaccination and for the following 6 days and vitamin D supplementation on the day of vaccination and once daily for the following 27 days
- Positive mood intervention on the day of vaccination and for the following 6 days
- Single dose oral vitamin D supplementation on the day of vaccination and once daily for the following 27 days

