9.9 Definition of end of study

The end of the study will be defined as the time the last blood sample is analysed.

10. Safety reporting

Safety reporting for participants in this study begins at the point of consent and ends at 168 days post-enrolment. Safety data will be collected via:

- Direct notification by the participant to the investigator via email or telephone according to the information on the study contact card given to each participant at enrolment.
- Investigator review of primary care medical records at 28 days and 168 days.

All serious adverse events that have not resolved by the end of the study, or that have not resolved upon discontinuation of a subject's participation in the study, must be followed until any of the following occurs:

- The event resolves
- The event stabilises
- The event returns to a baseline if a baseline value is available
- The event can be attributed to agents other than to study interventions or to factors unrelated to study conduct
- It becomes unlikely that any additional information can be obtained (participant or health care practitioner refusal to provide additional information, lost to follow-up after demonstration of due diligence with follow-up efforts)

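### The seven-day adverse event self-report instruction in section 9.3 contradicts the 168-day safety period in section 10 and covers only about a quarter of the vitamin D course

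*Protocol*

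**What the plan says.** Protocol section 9.3 (Enrolment visit) closes with the instruction to participants. They receive an email address and/or telephone number to "report any adverse events occurring in the seven days after vaccination". They also receive a 24-hour emergency number, but that is for advice about taking part and is not described as a route for reporting events.

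Section 10 (Safety reporting) sets a different period: "Safety reporting for participants in this study begins at the point of consent and ends at 168 days post-enrolment". It names two sources of safety data. One is direct notification by the participant, following the study contact card, with no seven-day limit stated. The other is "Investigator review of primary care medical records at 28 days and 168 days". Neither is restricted to serious events. Section 9 (Study Design) also says that adverse events will be recorded, without a time limit.

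The two interventions differ in length. The aims in section 6 refer to "vitamin D supplementation for 28 days and a brief positive mood intervention for 7 days in older adults". Section 9.3 says that participants allocated to the supplement "will be advised to buy and take this immediately prior to vaccination and once daily for the following 27 days". Section 7 gives the other course as "Positive mood intervention on the day of vaccination and for the following 6 days".

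Section 9.4 (Subsequent visits) describes blood sampling at days 28 and 168 and mentions no adverse event enquiry at those visits.

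**The concern.** Sections 9.3 and 10 are both current text and cannot both describe what participants are asked to do. A site reading section 9.3 would not ask for a mild event on day 15. A site reading section 10 would treat that event as inside the reporting period.

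The seven-day window is counted from vaccination and matches the length of the mood course. Vaccination, however, is usual care and not a study procedure (section 9.3), and section 10.4 assigns causality only to vitamin D and/or the mood intervention. For vitamin D, prompted reporting therefore stops about a quarter of the way through the exposure that the protocol intends to assess.

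The primary objective in the synopsis is feasibility and acceptability, and section 11.1 says the results are to shape a larger trial. With about 10 participants per arm at the planned pause, a few unreported mild events could change the picture of how the supplement was tolerated. A reporting procedure with this gap could also be carried into the larger trial.

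**Working it through.** No sample size, power or error rate is involved. The check is a day count followed by a comparison of the reporting routes.

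**Inputs**
- Self-report window: seven days after vaccination (section 9.3).
- Vitamin D: day 0 plus 27 daily doses (sections 7 and 9.3); stated as 28 days in section 6.
- Mood intervention: day 0 plus 6 days (section 7); stated as 7 days in section 6.
- Safety period: consent to day 168 (section 10).

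**The plan's own figures**
- Vitamin D: 1 + 27 = 28 days, which agrees with section 6.
- Mood: 1 + 6 = 7 days, which agrees with section 6.

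**Overlap of the window with the dosing days (days 0 to 27)**

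The protocol does not say whether the vaccination day counts, so three readings were tried.

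| Reading of the window | Dosing days inside | Dosing days outside | Share outside |
|---|---|---|---|
| Days 0 to 6 | 7 | 28 − 7 = 21 | 21/28 = 75% |
| Days 1 to 7 | 7 | 28 − 7 = 21 | 21/28 = 75% |
| Days 0 to 7 | 8 | 28 − 8 = 20 | 20/28 = 71% |

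**Overlap with the safety period**
- Seven-day window: (168 − 7)/168 = 161/168 = 95.8% outside.
- Eight-day window: (168 − 8)/168 = 160/168 = 95.2% outside.
- Of those 160 to 161 days, about 168 − 28 = 140 come after the last dose. This percentage therefore measures the disagreement between sections 9.3 and 10 and says little about missed exposure. The figure that concerns exposure is 71% to 75%.

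**What would capture a mild event on day 15 that is not taken to a GP?**
- The section 9.3 instruction: no, because the event is after day 7.
- Record review at day 28 (section 10): no, because nothing is in the record. Section 10.3 defines Grade 1 as needing no medical intervention and Grade 2 as needing none or minimal, so many such events need leave no trace in primary care.
- Direct notification (section 10): possible, but only if the participant volunteers it.
- The day-28 visit (section 9.4): no adverse event question is described.
- The e-diary (sections 7 and 9.3): unknown, because its content is not described. It counts for neither side.

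If the same event is taken to a GP, the day-28 record review should find it, whether or not it is serious.

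**The case against.** A reader might infer that non-serious events go unobserved for most of the vitamin D course. The protocol does not support that. Section 10 keeps both routes open to day 168, neither is limited to serious events, and the day-28 record review spans the whole course. Notification after day 7 is not forbidden. This part of the objection stands, and it limits the gap to mild events after day 7 that neither reach primary care nor are volunteered.

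Two further inferences also lack support. One is that vitamin D events come on gradually. The other is that the recorded events would mostly be vaccine reactions and so give false reassurance. The protocol says neither, and the point does not need them, since any mild event between day 8 and day 27 shows the gap.

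It is also fair to say that the study contact card is not available and may already carry the longer period. That would help in practice, but the protocol would still contradict itself, and the only instruction it describes at enrolment is the seven-day one. Participants are in contact with the study through reminders and the e-diary, and up to 20 may be interviewed about acceptability. None of this is described as adverse event collection.

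Finally, the synopsis lists no safety or tolerability endpoint, and the protocol plans no comparison of adverse event rates. That limits the consequence. It does not remove the conflict, because section 9 commits the trial to recording adverse events and how a 28-day supplement is tolerated bears on its acceptability.

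**Conclusion.** The point holds as a contradiction with a bounded consequence. Section 9.3 asks participants to report for seven days, while section 10 sets a period of 168 days. Taken as written, the section 9.3 instruction covers 7 to 8 of 28 vitamin D dosing days and leaves 20 to 21 (71% to 75%) outside it. After day 7, non-serious events rest on record review and unprompted notification, so mild events that do not reach a GP are likely to be under-reported. The protocol gives no event rates, so the number missed cannot be estimated.

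This rests on two assumptions: that the contact card repeats the section 9.3 window or is silent on it, and that the e-diary does not collect adverse events. If either is wrong, the practical loss is smaller, but the two sections still need to be reconciled. The matter should be corrected, but it does not threaten the primary objective.

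**What to change.** 1. Reconcile section 9.3 with section 10 so that participants are asked to report adverse events over the stated safety period. At minimum the request should cover the full 28-day course. Possible wording for section 9.3: *Participants will be asked to notify the study team of any adverse event from consent until day 168, using the details on the contact card.*
2. Make the study contact card state the same period.
3. Add to section 9.4 one adverse event question, identical in all four arms, at the existing day-28 and day-168 visits. Identical wording keeps the way of asking from creating differences between arms.
4. State in the protocol whether the e-diary collects adverse events.

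The cost is revised wording in the protocol and on the card, one CRF item at visits that already take place, and a few more adverse event entries to process. No new visit or sample is needed.
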